## **6.1 Labeling**

The blood collection tubes and the cryovials containing whole blood and plasma samples respectively will be labeled with subject number, date and time of sampling.

## **6.2 Bioanalytical Method**

A HPLC-MS-MS method capable of quantifying FP in human plasma at levels down to 1.5 picogram /mL (or better) will be used. Bioanalysis will be performed at Worldwide Clinical Trials (Austin, TX).

# **7. Statistical Methods and Analysis of Data**

## **7.1 Sample Size Calculation**

Using in-house and literature PK data for fluticasone propionate, the variability in the PK parameters  $C_{max}$  and  $t_{max}$  were estimated to be between 20% to 40% (%CV). If the %CV is 30% and the products differ by only 5%, a sample size of 40 (no dropouts) was initially thought to be appropriated to have 80% power to show that the products are equivalent.

$$N = 2(t_{\alpha,2N-2} + t_{\beta,2N-2})^2 * [CV/(V - \delta)]^2$$

N = total number of subjects required to be in the study

t = the appropriate value from the t distribution

$\alpha$  = the significant level

1- $\beta$  = the power, usually 80%

CV = the coefficient of variation

V = the bioequivalence limit ( $\ln 1.25 = 0.223$ )

$\delta$  = the difference between the products (for 5% difference, delta equals ( $\ln(1.05) = 0.0488$ )

However, due to budgetary constraints, the sample size was re-assessed and it was determined that the minimum number of subjects necessary to complete the study is approximately 22 subjects (considering 10% dropout rate, 24 subjects will be recruited). This sample size number does not affect the study design, which is kept as a four-way crossover (i.e., no study drug was removed from the study), and is sufficient to be utilized to achieve 80% power to show that the products are equivalent, as shown in the table below.

Case	Test / Reference Ratio (point estimator)	Intra-Individual Variability (ANOVA-CV)	Power	Sample Size (without dropouts)	Dropout Rate	Final Sample Size
1	0.95	30%	80%	40	~10%	44 (previous sample size)
2	0.95	21%	80%	22	~10%	24 subjects
3	1.00	24%	80%	22	~10%	24 subjects
4	1.05	22%	80%	22	~10%	24 subjects

**Safety Population:** All subjects randomized who received at least one dose of study drugs.

**Study Population to be Analyzed:** Analyses and summaries of pharmacokinetic data will be based on subjects who are administered all doses, complete at least 75% of blood sampling and follow the protocol procedures.

**Data Analysis:** Once the bioanalytical data is available, the pharmacokinetic data analysis will be conducted under blinded conditions. Afterwards, formulation-based analysis will be conducted under unblinded conditions.

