## 7.2 *Non-Compartmental Analysis (NCA)*

Hypothesis of the proposed research is that the three test formulations (differing in the c/p ratio) will differ in AUC and Cmax estimates. Three multiple comparisons will be performed i.e. Reference against the reference, reference against test 1 and reference against test 2. A multiplicity adjustment (e.g. bonferroni type) will be made for the 3 multiple comparisons. No additional adjustment will be made for the use of multiple metrics. NCA will be performed in WinNonlin using an inbuilt extra-vascular PK model. Standard PK metrics such as  $AUC_{(0-30min)}$ ,  $AUC_{(0-t)}$ ,  $AUC_{(0-inf)}$ ,  $C_{max}$ ,  $t_{max}$ , terminal slope/half-life,  $CL/F$ ,  $Vdss/F$ ,  $AUMC_{(0-t)}$ ,  $AUMC_{(0-inf)}$ , and MRT will be calculated for each individual plasma-concentration-time profile. ANOVA model will be used to construct univariate 90% confidence intervals for  $AUC_{(0-t)}$  and  $C_{max}$  ratios and applied to conventional 0.8 – 1.25 average BE limits. If needed, alternative BE evaluation methodology and or BE criteria may be investigated. Data will also be assessed by ANOVA methods (SAS 9.2 or another equally suitable software package) to test for statistical differences ( $p<0.05$ ).

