Data analysis plan

Pharmacokinetic Comparison of Locally Acting Orally Inhaled Drug Products ('DPI study', FDA BAA-16-00122)

1. Purpose

This document describes the non-compartmental data analysis plan for the above mentioned clinical trial. This clinical pharmacokinetic (PK) study assessed three fluticasone propionate DPI formulations (formulation 1, 2, 3) which have been characterized through *in vitro* methods. These formulations were compared in the present double-blind, randomized 4-way cross-over study; one formulation was repeated to evaluate intra-subject variability; this replicated formulation is named 3a and 3b.

2. Objectives

The primary aim of this research study is to aid the FDA in finding methods to ensure that the versions of generic drugs that are inhaled (for example, drugs used to treat asthma) are bioequivalent to the trade name drug. As a part of the research study, pharmacokinetic (PK) studies (studies measuring drug levels in the blood over time after inhalation) will be done using three different versions of fluticasone propionate (FP, a drug routinely used in asthmatic patients) administered using a dry powder inhaler (DPI, an inhalation device that delivers the drug as a dry powder).

3. Available *in vitro* data and proposed normalization

We will use the formulation with the largest Median Mass Aerodynamic Diameter (MMAD) as reference (**Table 1**).

Table 1: Summary of FPD data averaged over the 12 and 20 month time points

Formulation	FPD (<5 µm) (µg)	FPD (<3 µm) (µg)	MMAD (µm)
15-mm-016	18.707	9.977	3.77
15-mm-017	12.230	5.274	4.53
15-mm-015	15.869	8.599	3.73

We expect that the c/p ratio is determined by the MMAD with larger particles being deposited more centrally compared to smaller particles.

We will use three approaches of normalizing the PK parameters:

- 1) Normalization based on the ex-throat data
- 2) Normalization based on fine particle dose (FPD <3 µm) data
- 3) Normalization based on fine particle dose (FPD <5 µm) data

Normalization factors for the ex-throat data will be calculated separately for the VCU, AIT and OPC throats. The average normalization factors over the three throats will be used for the normalization using this approach. The normalization factors from this ex-throat approach will be used for the **primary analysis**.

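### Protocol 7.2 and SAP 4.2 do not settle whether the equivalence intervals are adjusted for multiplicity, and the 80% power in Protocol 7.1 reproduces only without adjustment

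*Protocol*

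**What the plan says.** **Power (Protocol 7.1).** The number of completers was first set at 40, for a CV of 30% and a 5% difference. The text continues: "However, due to budgetary constraints, the sample size was re-assessed". The new number is 22 completers, 24 recruited, which "is sufficient to be utilized to achieve 80% power to show that the products are equivalent, as shown in the table below". The table gives 22 for ratio 0.95 with CV 21% (Case 2), ratio 1.00 with CV 24% (Case 3) and ratio 1.05 with CV 22% (Case 4). Case 1 keeps CV 30% with 40. The symbol alpha is defined but given no value.

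**Multiplicity (Protocol 7.2).** "Three multiple comparisons will be performed i.e. Reference against the reference, reference against test 1 and reference against test 2". Then: "A multiplicity adjustment (e.g. bonferroni type) will be made for the 3 multiple comparisons". The same paragraph says "ANOVA model will be used to construct univariate 90% confidence intervals for" AUC(0-t) and Cmax ratios, and adds ANOVA methods "to test for statistical differences" at p<0.05.

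**SAP.** Section 3 states: "We will use the formulation with the largest Median Mass Aerodynamic Diameter (MMAD) as reference". By its Table 1 that is 15-mm-017. Section 4.2 makes the larger-MMAD product the reference within each pair. Its Table 2 has six comparisons with replicates 3a and 3b of 15-mm-015 kept separate, and a 90% interval is planned for each. Multiplicity is not mentioned.

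**The concern.** A power statement holds at one alpha, and the plan does not fix that alpha for the equivalence tests. Three things are open.

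- **What is adjusted.** Protocol 7.2 promises an adjustment but prints 90% intervals, which are unadjusted, beside difference tests at p<0.05. It does not attach the adjustment to either.
- **Which family.** The Protocol counts three comparisons; the SAP lists six.
- **Which reference.** A comparison of the reference with itself needs a replicated reference, and only FPF III is given twice. The Protocol therefore implies FPF III. In the SAP the replicated product is 15-mm-015, while the overall reference is 15-mm-017.

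Two things are at stake. First, whether a pair is declared bioequivalent can depend on whether 90% or 96.7% intervals are used. Second, Protocol 7.2 hypothesises that the formulations differ, so the comparison most expected to pass is FPF III against its replicate. That control has power well below 80% at Case 3's CV if the adjustment reaches the equivalence intervals.

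**Working it through.** **Inputs.** n = 22, with the ratios and CVs of Cases 2–4 (Protocol 7.1). Limits are ±ln 1.25 = ±0.2231 (Protocol 7.2). The ANOVA has treatment, period, sequence and subject-within-sequence effects (SAP 4.2).

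**Formulas.**
- σ = √ln(1+CV²). This gives 0.2077 (21%), 0.2174 (22%) and 0.2366 (24%).
- SE = σ√(2/n) when one replicate is compared with one other treatment: 0.0626, 0.0656 and 0.0714.
- SE = σ√(1.5/n) when both FPF III replicates are pooled as reference, because the variance is σ²(1/n + 1/2n).
- Residual df for the four-way ANOVA: 88 observations − 1 − 21 (subjects) − 3 (periods) − 3 (treatments) = 60. For a two-treatment crossover: 22 − 2 = 20.
- Power is that of two one-sided tests, integrated over the chi-square distribution of the residual variance.

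**Step 1: reproduce the table.** At one-sided 0.05 with df N−2, the smallest even N reaching 80% is 22 in Cases 2, 3 and 4, and 40 in Case 1 (power 81.6%). One-sided 0.025 would need 24–28 for Cases 2–4, so it does not give 22 throughout. The table is an unadjusted 0.05 calculation.

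**Step 2: apply the adjustment.** Bonferroni for three gives 0.05/3 = 0.0167 one-sided, a 1 − 2(0.0167) = 96.7% interval. Power per comparison and per metric at n = 22:

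| Setting | Case 2 | Case 3 | Case 4 |
|---|---|---|---|
| Unadjusted, df 20 | 83.7% | 83.1% | 81.3% |
| Unadjusted, df 60 | 85.4% | 85.2% | 83.1% |
| Bonferroni, separate, df 60 | 69.9% | 65.3% | 65.9% |
| Bonferroni, separate, df 20 | 65.4% | 58.9% | 61.0% |
| Bonferroni, FPF III pooled, df 60 | 83.4% | 84.3% | 80.7% |

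The pooled row applies only to comparisons against FPF III. It does not help III against III*, nor SAP comparison 1 (016 against 017).

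**Step 3: the FPF III control (ratio 1.00, df 60).** With Bonferroni, power is 83% at CV 21%, 77% at CV 22% and 65% at CV 24%. Unadjusted at CV 24% it is 85%.

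**Step 4: effect on a conclusion.** Suppose the observed CV is 24% (SE 0.0714, df 60).
- 90% interval: half-width 1.671 × 0.0714 = 0.119. Equivalence needs a log ratio within ±(0.223 − 0.119) = ±0.104, a point estimate of about 0.90–1.11.
- 96.7% interval: half-width 2.178 × 0.0714 = 0.156. The log ratio must lie within ±0.068, about 0.93–1.07.

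Estimates between these bounds pass under one rule and fail under the other.

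**Step 5: CV at which power is 80%, n = 22 (df 20 to 60).**

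| Setting | Ratio 0.95 | Ratio 1.05 | Ratio 1.00 |
|---|---|---|---|
| Unadjusted | 22.1–22.7% | 22.4–22.9% | 24.8–25.4% |
| Bonferroni, separate | 18.1–18.9% | 18.4–19.2% | 20.7–21.5% |
| Bonferroni, pooled (df 60 only) | 21.9% | 22.2% | 25.0% |

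At the initial planning CV of 30%, unadjusted power with 22 completers is 50–53% at ratio 0.95 and 57–60% at ratio 1.00.

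**The case against.** **The table is correct and conditional.** A reader might infer that 7.1 contains an arithmetic error. It does not. The sentence points to a table with printed ratios and CVs, and Case 1 shows that a CV of 30% needs 40. The only gap is that the calculation takes no account of the adjustment promised in 7.2.

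**The true power is not shown to be 59–70%.** A reader might infer that it is. That range requires the adjustment to fall on the equivalence intervals and each FPF III replicate to be used separately, as in SAP Table 2; its low end also needs df 20 rather than the four-way ANOVA's 60. The Protocol's count of three fits a pooled reference or one chosen replicate, since separate replicates would make five comparisons. Pooling restores 81–84% for the test products. One chosen replicate gives the separate figures. Neither document says which.

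**The adjustment may concern only the difference tests.** It follows directly on a hypothesis of difference, and every printed interval is 90%. This reading is reasonable, and 81–85% then stands. But 7.2 attaches the adjustment to the comparisons without naming the analysis.

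**The SAP does not reject adjustment.** It is silent, so a flat contradiction on alpha would be too strong a reading. The differences in family and reference are explicit in the SAP and implied by 7.2.

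**Bonferroni is only an example.** Simulated Holm power with separate replicates (df 60) is 77–81% for the test comparisons. For the control at CV 24% it is 78–82% if the other comparisons are also at ratio 1.00. If those fail, as hypothesised, the control is tested at 0.05/3 and returns to about 65%.

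**The CVs are not unsupported.** 21–24% lies within the 20–40% range that 7.1 attributes to in-house and literature data. No source is given for those particular values, and no CV is given for AUC(0-t). These are missing details only.

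**Enrolment is unaffected.** The SAP describes the study partly in the past tense, so restating power changes no recruitment decision. That is so; the analysis rule still matters.

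**Conclusion.** The concern holds as an inconsistency between the multiplicity rule and the power statement, and should be fixed. The 80% in 7.1 is right for its tabulated ratios and CVs at unadjusted one-sided 0.05 (81–85%). If Bonferroni for three reaches the equivalence intervals, power is 65–70% under the four-way ANOVA with separate replicates (59–65% at df 20). With FPF III pooled it is 81–84% against FPF III, while III against III* remains at 65% at CV 24%. If only the difference tests are adjusted, nothing in 7.1 is lost.

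These figures assume 22 completers, a common within-subject variance, and power counted per comparison and per metric. The 0.05 is inferred from reproducing the table, and FPF III as the Protocol's reference is inferred from the replication. The documents do not show which branch applies, and that is the defect.

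**What to change.** Text only.

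1. **Protocol 7.2 and SAP 4.2**, before the unblinding described in SAP 4.1: state one rule. It should name the family (three or six comparisons) and the reference, say whether the equivalence intervals or only the difference tests are adjusted (90% or, for three comparisons, 96.7% intervals), and say whether the FPF III replicates are pooled.
2. **Protocol 7.1**: restate the power at that alpha, conditional on CV.
   - *Unadjusted:* at least 80% per comparison and metric up to a CV of about 22% (ratio 0.95 or 1.05) or 25% (ratio 1.00). At CV 30%, about 50–53% (ratio 0.95) or 57–60% (ratio 1.00).
   - *Bonferroni, separate replicates:* ceilings of about 18–19% and 21–22%.
   - *Bonferroni, pooled:* about 22% and 25% for the test products against FPF III only. III against III* keeps the separate-replicate ceiling of 21–22%.
3. **Side note for 7.1:** give the source of the 21–24% values and a CV for AUC(0-t), or say that none is available.

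The cost is a possibly less favourable power statement. No subjects are added and the design does not change.

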4.1. Non-compartmental pharmacokinetic analysis

Non-compartmental analysis (NCA) will be performed as described previously.¹ The NCA PK parameters will be calculated for each subject and study period using the formulas implemented in the Phoenix / WinNonlin Professional software. Whenever possible, at least three observations above the quantification limit will be used to estimate the terminal slope. The ANOVA statistics will be calculated for Cmax, AUC_{0-last}, and AUC_{0-inf}. Descriptive statistics will be calculated and reported for all PK parameters.

The NCA PK parameters will be calculated and NCA PK results sent to the FDA colleagues **before unblinding**. Summary statistics will be calculated after subsequent unblinding.

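### The 80% power in protocol section 7.1 holds for one metric but is worded as power to show the products equivalent, while section 7.2 applies the limits to both AUC(0-t) and Cmax

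*Protocol*

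**What the plan says.** Protocol section 7.1 starts from variability: "Using in-house and literature PK data for fluticasone propionate, the variability in the PK parameters" Cmax and tmax was put at 20% to 40%. After a cut for budget reasons, it states that "the minimum number of subjects necessary to complete the study is approximately 22 subjects" and calls this number "sufficient to be utilized to achieve 80% power to show that the products are equivalent". The table supports this with three cases at 22 completers: ratio 0.95 with CV 21%, ratio 1.00 with CV 24%, and ratio 1.05 with CV 22%. Neither the table nor the printed formula provides for a second metric.

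Protocol section 7.2 describes the equivalence assessment: "ANOVA model will be used to construct univariate 90% confidence intervals for" the AUC(0-t) and Cmax ratios, to be compared with the "conventional 0.8 – 1.25 average BE limits". On multiplicity it plans a Bonferroni-type adjustment for three comparisons and adds: "No additional adjustment will be made for the use of multiple metrics".

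SAP section 4.1 lists three metrics: "The ANOVA statistics will be calculated for Cmax", AUC to the last quantifiable concentration and AUC to infinity. The SAP gives no acceptance limits and no power.

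**The concern.** The sentence in 7.1 is about products, but the calculation is about one metric. If a pair of products is called equivalent only when both intervals lie within the limits, the chance of reaching that verdict is at most the smaller of the two single-metric powers, and usually less.

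The variability inputs do not settle how much less. The quoted CV range is for Cmax and tmax. tmax has no equivalence test in 7.2, while AUC(0-t), which is tested, has no CV in either document.

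What is at stake is how a failed comparison is read. The study asks whether PK can detect differences between formulations, so a reader needs to know how often a pair with a true ratio near 1 would miss the limits through imprecision alone. Taking 80% as the power of the overall verdict could understate that rate.

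**Working it through.** **Inputs.** From 7.1: n = 22 completers and the ratio and CV of Cases 2 to 4. From 7.2: 90% intervals, equivalent to two one-sided tests at 0.05 each, and limits ±ln 1.25 = ±0.223. From SAP 4.2: an ANOVA with treatment, period, sequence and subject within sequence.

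**Formulas.** On the ln scale, σ = √ln(1 + CV²) and SE = σ√(2/n). Error df are n − 2 = 20 for a two-treatment analysis. If all four periods are pooled, they are 88 − 1 − 21 (sequence and subjects) − 3 (period) − 3 (treatment) = 60. The documents do not say which applies, so both are shown.

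**Step 1: reproduce the plan's figure.** For Case 2, σ = √ln(1 + 0.21²) = 0.208 and SE = 0.208 × √(2/22) = 0.0626. The distance from ln 0.95 = −0.051 to the nearer limit is 0.172, or 2.74 SE. Subtracting t(0.95, 20) = 1.72 leaves 1.02, which gives power of roughly 0.84. The exact calculation gives 83.7%.

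With n − 2 df, the exact single-metric calculation gives a smallest even N of 40, 22, 22 and 22 for Cases 1 to 4, matching the table. The printed formula, solved iteratively, does not: it gives about 38, 19, 15 and 20, or 53, 26, 21 and 28 with β/2. The table is therefore consistent with an exact one-metric calculation.

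**Step 2: joint power, both metrics with the tabulated ratio and CV.** This comes from 1,000,000 simulated trials per setting, with correlated estimates and correlated error variances. Both intervals must lie within the limits.

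| Case (ratio, CV) | Error df | One metric | Joint, correlation 0 | 0.5 | 0.8 | 0.9 |
|---|---|---|---|---|---|---|
| 2 (0.95, 21%) | 20 | 83.7% | 70% | 74% | 77% | 79% |
| 2 | 60 | 85.4% | 73% | 76% | 79% | 81% |
| 3 (1.00, 24%) | 20 | 83.1% | 69% | 71% | 75% | 77% |
| 3 | 60 | 85.2% | 73% | 75% | 78% | 80% |
| 4 (1.05, 22%) | 20 | 81.3% | 66% | 70% | 74% | 76% |
| 4 | 60 | 83.1% | 69% | 73% | 76% | 78% |

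The correlation-0 column can be checked by squaring. For Case 4 with 20 df, 0.813² = 0.661; for Case 2 with 60 df, 0.854² = 0.729. As the correlation approaches 1, joint power returns to the one-metric value.

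**Step 3: vary the second metric's CV, same ratio.**
- 20% below the tabulated CV: about 76–85% (correlation 0–0.9, 20 or 60 df).
- 20% above it: 57–70% (correlation 0.3–0.9, 60 df).
- A second-metric CV of 15%: 80–85%.

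**Step 4: the α used.** All figures above use 0.05 per side. If the Bonferroni-type adjustment in 7.2 also applies to the equivalence intervals (0.05/3 per side), single-metric power at 22 completers is 59–65% (20 df) or 65–70% (60 df). Joint power with equal CVs is then about 35–63%.

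**The case against.** The strongest reply is that nothing has been miscalculated. The table reproduces exactly, and its own inputs give 81–85%. A reader might infer from the joint figures that the table is wrong, or that power is below 80% at the tabulated inputs. The documents do not support that. A value below 80% needs assumptions they do not state: that both metrics must pass, that AUC has the tabulated CV, that both metrics share the same true ratio, and that their correlation is below roughly 0.84–0.98, depending on case and df. The ratio assumption matters too: if AUC's true ratio is 1.00 in Case 2, joint power is roughly 78–83%. All of this stands, and is why the joint figures can only be conditional.

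A reader might also take the both-must-pass rule as given, as the reason for making no adjustment across metrics. Section 7.2 gives no such reason and calls the intervals univariate. Requiring both is the natural reading of a claim that products are equivalent, but it remains an inference.

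Finally, a reader might infer that a failed 3a versus 3b comparison would be mistaken for a formulation difference. That is weak: both arms are the same formulation, and the replicate exists to guard against that error. At a true ratio of 1.00 with equal CVs, joint power is 86–92% for CV 21% and 81–88% for CV 22%. It falls below 80% in most settings only at CV 24%.

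What survives is the mismatch between the wording of 7.1 and the two-metric assessment in 7.2, together with the missing AUC variability.

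**Conclusion.** The concern holds as a matter of what the stated power describes, not as an arithmetic error. The 80% is correct per metric and should not be read as the power of a verdict on two metrics.

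Under a both-must-pass rule, with the tabulated ratio and CV for each metric and α of 0.05 per side, joint power is 66–79% (20 df) or 69–81% (60 df) for correlations 0 to 0.9. The loss against the one-metric value is at most about 15 points (Case 4, 20 df: 81.3% against 66%). It shrinks to little or nothing if the second metric is clearly less variable or the correlation is very high, and grows if the second metric is more variable. The documents cannot show which situation applies, because they give neither an AUC CV nor a correlation.

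**What to change.** In protocol section 7.1:

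- State that the tabulated 80% is per metric, and name the metric that the CV describes. If it was meant as the CV of the more variable metric, say so.
- State whether concluding equivalence requires both AUC(0-t) and Cmax to meet the limits.
- Base planning variability on the tested metrics, Cmax and AUC(0-t), instead of tmax. The AUC figure should come from the sponsor's own data; the 20–40% range should not be carried over to AUC.
- Report joint power as a conditional range with its assumptions: CVs, ratios, correlation, error df, and α of 0.05 without the Bonferroni-type adjustment. Add that power is lower if that adjustment applies to the equivalence intervals.

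Leave the sample size unchanged. The cost is some wording and a short recalculation, with no extra subjects or procedures. The downside is a somewhat less favourable stated power.
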